6.3 Study procedures – HCV treatment

During HCV treatment and in the follow-up period, patients will undergo monitoring for treatment adherence, and complete interval surveys for risk assessment, urine drug screens, HIV antibody/antigen testings, and HCV RNA levels. Blood samples for storage and research may be obtained (PBMC, plasma, serum and Paxgene RNA). Patients may undergo serial evaluation of liver fibrosis with fibroscan. See Appendix A Study Schedule.

6.3.1 Adherence monitoring

On weeks 4, 8, 12 participants will meet with study staff to complete counts of remaining pills, as well as answering questions regarding HCV treatment adherence.

6.3.2 Risk assessments

At screening patients will complete a baseline epidemiologic survey (Appendix C). Patients will also complete interval risk assessments with the HIV Risk-taking Behavior Scale (Appendix D) at weeks 4, 12, 24, 48, 72 and 96. Assessments will be administered by study staff at the time of study visit. As part of standard practice at the HIPS site, patients will be asked about their use of the syringe exchange program (SEP) at those visits. AUDIT-C brief alcohol screen will be administered at the time of fibroscan at weeks 24, 48 and 96 (Appendix E). Additionally at screening, week 12, and week 24 the validated 16-item HCV-PRO questionnaire will be administered (Appendix F). This version of the HCV-PRO questionnaire was developed to be self-administered for persons with a diagnosis of chronic hepatitis viral infection, including treatment naïve, currently treated, and previously treated but who have remained infected in an attempt to assess change in patient reported outcomes prior to treatment, during treatment, and after treatment completion. At week 24 or next possible time point, participants will be administered the validated Adverse Childhood Experience (ACE) Questionnaire (Appendix H) which has shown to be a significant risk factor for substance use disorders and will better inform our understanding of the study population.

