2.2 Secondary Objective

1. Evaluate uptake of PrEP
2. Evaluate adherence to PrEP
3. Evaluate uptake of buprenorphine when clinically indicated (HIPS site only)
4. Evaluate retention in buprenorphine programs (HIPS site only)
5. Assess change in risk behaviors at baseline, during, and after HCV treatment

6. Evaluate the impact of active IDU vs non-injecting opioid misuse on efficacy of DAAs for the treatment of HCV
7. Evaluate the impact of OST on HCV treatment outcomes

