6.2 Standard of care HCV treatment

All participants will be started on HCV treatment after confirming eligibility on Day 0. Patients will complete visits and laboratory monitoring as per standard of care guidelines.

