6.3.4 Stored sample collection

Blood samples for storage and research will be obtained at screening, total of 11 tsp, and a total of 9 tsp at weeks 4, 12, 24, 48 and 96. Samples collected will include:

- Serum storage (10 mL) SST/tiger top (2 teaspoons)
- Plasma storage (6ml) EDTA (1 teaspoon)
- DNA paxgene will be collected (8.5ml) one time at baseline (1 ½ teaspoon)
- RNA paxgene will be collected (2.5ml) (1/2 teaspoon)
- Peripheral blood mononuclear cells (30 ml) Green top/heparin (6 teaspoons)

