10.1 Return of Withdrawn/Removed Subjects

A participant who has withdrawn may not return to the study.

11 Remuneration Plan for Subjects

Participants will not be renumerated for receiving HCV treatment.

Participants will not be renumerated for standard of care PrEP or buprenorphine.

Participants will receive \$25 remuneration as gift cards at those visits where HIV risk assessment and stored sample blood draws are completed. Those 7 visits are Screening, Week 4, Week 12, Week 24, Week 48, Week 72 and Week 96 only. For adherence visits for PrEP which DO NOT coincide with HIV risk assessment or stored sample visits, participants will receive \$25 renumeration as gift cards for those visits. This would be a maximum of 6 additional visits at \$25/visit. We will encourage combined visits.

Participants who choose to enroll in the GMA will be renumerated as follows:

Compensation for GMA data collection	A) Weeks 1-24 Participants can receive a total of \$480 between weeks 1-24 for answering random daily prompts based on how many prompts they answer in each week: Answering 1-7 prompts/week = \$5 Answering 8-14 prompts/week = \$10 Answering 15-21 prompts/week = \$15 Answering 22-28 prompts/week = \$20 B) Weeks 25-48	Up to \$920.00
--------------------------------------	--	----------------

	
Participants can receive a total of \$240 between weeks 25-48 for answering random daily prompts based on how many prompts they answer each week:
 
Answering 1-3 prompts/week = \$5
 
Answering 4-7 prompts/week = \$10
 
C) End of Study Week 48
 
Participants can receive up to \$200 for returning the smartphone in working condition at Week 48, to be pro-rated by week for those participants who do not complete 48 weeks of the study,
	
--	--	--

12 Monitoring

As this is an observational study with intervention limited to blood and epidemiologic data collection, safety issues are not expected. PI and the study team will conduct regular monitoring of safety on a weekly basis and report to the IRB as specified in section 9.

13 Statistical Considerations

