APPENDIX B: Study Schedule

					M1	M2	M3	M6	M9	M12	M18	M24
HCV Treatment	Screening	Day 0	Week 2	Week 3	Week 4	Week 8	Week 12	Week 24	Week 36	Week 48	Week 72	Week 96
MD Visit	X	X*			X*	X*	X*	X*				
HCV SOC Labwork	X				X		X	X				
HCV RNA	X				X		X	X		X	X	X
HCV Adherence			X		X	X	X					
Stored Samples	X				X		X	X		X		X
Fibroscan	X							X		X		X
PrEP Retrospective Questionnaire										X	X	X
PrEP**		Day P0			Week P4		Week P12	Week P24	Week P36	Week P48		
MD Visit		X			X		X	X	X	X		
Adherence					X		X	X	X	X		
Labwork		X			X		X	X	X	X		
Buprenorphine***		Day B0	Week B2		Week B4	Week B8	Week B12	Week B24	Week B36	Week B48		
MD Visit		X	X		X	X	X	X	X	X		
Urine Buprenorphine			X		X	X	X	X	X	X		
Assess Retention			X		X	X	X	X	X	X		
Risk Monitoring	Screening	Day 0	Week 2	Week 3	Week 4	Week 8	Week 12	Week 24	Week 36	Week 48	Week 72	Week 96
Epidemiologic Survey	X											
HCV PRO	X						X	X				
HIV Risk/SEP Assessment		X			X		X	X		X	X	X

Urine Drug Screen	X				X		X	X		X	X	X
HIV 4 th gen	X				X		X	X		X	X	X
AUDIT-C	X							X		X		X
ACE								X				
GMA Assessment****												
GMA Training and Cell Distribution		X										
Adherence Packet -4		X										
Adherence Packet-2					X		X	X		X		
Return Cell Phone										X		

*Study participants will be offered PrEP and buprenorphine at every MD visit if have not currently uptaking

**PrEP uptake is optional. Day P0 can be on any day from Day 0 to Week 24 of HCV treatment.

***Buprenorphine uptake is optional. Day B0 can be on any day from Day 0 to Week 24 of HCV treatment.

****GMA participation is optional.

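### Section 6.3.2 starts the HIV risk scale at Week 4 while Appendix B starts it at Day 0, so the pre-treatment score for Secondary Objective 5 depends on which text staff follow

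*Combined protocol and SAP*

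**What the plan says.** Secondary Objective 5 (Section 2.2) is to "Assess change in risk behaviors at baseline, during, and after HCV treatment".

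Section 6.3.2 names two instruments that bear on risk behaviour. The first is a survey: "At screening patients will complete a baseline epidemiologic survey (Appendix C"). The second is the scale, given as "interval risk assessments with the HIV Risk-taking Behavior Scale (Appendix D) at weeks 4, 12, 24, 48, 72 and 96". The section mentions no administration of the scale at Screening or Day 0.

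Section 6.2 fixes the start of treatment: "All participants will be started on HCV treatment after confirming eligibility on Day 0".

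In Appendix B, the row "HIV Risk/SEP Assessment" is marked at Day 0 and at weeks 4, 12, 24, 48, 72 and 96. Its Screening cell is empty.

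Section 11 pays $25 "at those visits where HIV risk assessment and stored sample blood draws are completed" and closes the list: "Those 7 visits are Screening, Week 4, Week 12, Week 24, Week 48, Week 72 and Week 96 only".

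Section 13.1 gives a summary method for PrEP and buprenorphine outcomes. It names no baseline visit and no analysis for change in risk behaviour.

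**The concern.** The study is open label and non-randomized, with no untreated comparison group. The natural reference for change in risk behaviour is therefore each participant's own score on the same scale before treatment. Section 6.3.2 and Appendix B disagree on whether that score is collected.

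Under the 6.3.2 text the first score comes four weeks into antiviral treatment. PrEP and buprenorphine are optional and may start on any day from Day 0 to Week 24, so some participants will also have started one or both by then. Any shift in behaviour over the first four weeks would be absorbed into the reference value. A missed pre-treatment score cannot be collected afterwards.

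Section 11 does not settle the matter. It omits Day 0, the visit where Appendix B places the assessment, so the payment list gives staff no cue to administer the scale then.

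**Working it through.** The check compares visit lists. No sample-size or power formula applies.

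**Inputs.** Scale visits from Section 6.3.2; risk-assessment row from Appendix B, read column by column against its own header (header and row each have 13 fields, so the Day 0 mark is not a shifted cell); stored-sample visits from Section 6.3.4, which agree with the Appendix B row; paid visits from Section 11.

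| Source | Screening | Day 0 | Wk 4 | Wk 12 | Wk 24 | Wk 48 | Wk 72 | Wk 96 | Visits |
|---|---|---|---|---|---|---|---|---|---|
| 6.3.2, risk scale | – | – | X | X | X | X | X | X | 6 |
| Appendix B, risk assessment | – | X | X | X | X | X | X | X | 7 |
| 6.3.4, stored samples | X | – | X | X | X | X | – | X | 6 |
| Section 11, paid visits | X | – | X | X | X | X | X | X | 7 |

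**Step 1: the plan's own figure.** Section 11 states 7 visits. Screening plus six weeks is 1 + 6 = 7, so the list agrees with its own count.

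**Step 2: 6.3.2 against Appendix B.** 7 − 6 = 1, and the visit that differs is Day 0. It is the only pre-treatment administration of the scale in either place.

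**Step 3: what Section 11 implies.** Read literally, the list covers visits where both procedures are done, which would put the scale at Screening. That reading fails at Week 72, which is on the list but has no stored-sample draw. Even with the scale added at Screening, the visits with both procedures would be Screening and weeks 4, 12, 24, 48 and 96, which is 6 and not 7.

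Read as visits with either procedure, the 6.3.2 scale visits and the stored-sample visits share weeks 4, 12, 24, 48 and 96 (5 visits). The count is 6 + 6 − 5 = 7, and the set is exactly the Section 11 list. Screening is then explained by the blood draw (Section 6.3.4: "Blood samples for storage and research will be obtained at screening, total of 11 tsp, and a total of 9 tsp at weeks 4, 12," and on to week 96). On this reading Section 11 matches 6.3.2 and has no pre-treatment scale.

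On both readings Day 0 is absent from Section 11.

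**Step 4: after reconciliation to Day 0.** Appendix B risk visits and stored-sample visits again share 5, so visits with either procedure number 7 + 6 − 5 = 8, against the 7 that Section 11 pays for.

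**Step 5: whether another measure can stand in.** The epidemiologic survey (Appendix C) is a different form from the scale (Appendix D), and the items of both are not shown in the available text. The urine drug screen is taken at Screening and repeated, so it supports change in drug-screen results, but it does not yield a score on the scale.

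**The case against.** The strongest reply is that a baseline is already planned. Section 6 sends staff to Appendix B, which schedules the assessment at Day 0. Section 6.3.2 calls its list interval assessments, sets it beside a baseline survey, and does not say that the list is exhaustive. Read together, the text could be listing follow-up visits while the schedule supplies Day 0. AUDIT-C shows the same pattern: 6.3.2 gives weeks 24, 48 and 96, and Appendix B adds Screening.

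This has weight, and it is why the baseline is exposed rather than absent. It does not remove the conflict. For other instruments Section 6.3 states the pre-treatment visit outright: the epidemiologic survey, the HCV-PRO and the urine drug screen are all placed at screening. A reader of the text has no signal that the risk scale differs. The AUDIT-C gap shows that text and schedule diverge on more than one instrument, which is a reason to reconcile them.

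A second reply is that Objective 5 concerns risk behaviours generally and names no scale, so the screening survey and drug screen give a baseline of a kind. That is right as far as it goes. The loss under 6.3.2 would be confined to change on the scale; change in every risk behaviour would not become inestimable.

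A reader might also infer that three sections give three different first assessments: Week 4, Day 0 and Screening. The documents do not establish this, because Section 11's Screening entry may be there for the blood draw alone. A worry that some participants would have a Screening baseline and others a Day 0 one rests on the same unproven reading.

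**Conclusion.** The inconsistency between Section 6.3.2 and Appendix B is real and is one visit wide: six administrations of the scale against seven, the difference being the only pre-treatment one. Section 11 omits that visit on any reading.

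The consequence is conditional. If staff follow 6.3.2, change on the scale runs from Week 4. If they follow Appendix B, a Day 0 score exists. A reader might infer that none of the 200 participants will have a baseline score. That is the extreme case, in which every site ignores the visit schedule, and the documents do not support treating it as the expected outcome. Nor do they support saying that every participant will be on PrEP or buprenorphine by Week 4, since both are optional and may start as late as Week 24.

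The conclusion assumes that the screening survey does not reproduce the scale's items. If it did, the loss would be smaller; the forms are not shown, so this cannot be checked. The effect is limited to Secondary Objective 5. The point is still worth correcting because an uncontrolled study has no other same-instrument reference for this objective, and a missed score cannot be recovered.

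**What to change.** 1. Amend Section 6.3.2 to list Day 0 ahead of weeks 4, 12, 24, 48, 72 and 96, and state that the Day 0 scale is completed before the first antiviral dose. This matches Appendix B, which fixes the day but not the order within it.
2. In Section 13.1, define change on the scale for Secondary Objective 5 as change from the Day 0 score.
3. Reconcile Section 11: state whether Day 0 is a paid visit, making 8 rather than 7 visits with either procedure, or whether the Screening payment covers it.
4. For participants already enrolled, record whether a score was obtained before the first dose and at which visit, report how many have one, and do not present a Week 4 score as a baseline.

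The cost is wording in three sections. No procedure is added to the Appendix B schedule. If Day 0 is paid at the existing $25 rate, the most it adds is 200 × $25 = $5,000 across all treated participants; if the Screening payment covers it, there is no added payment, but participants complete an assessment at a visit with no payment of its own.

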6.3.3 Urine drug screen

Urine will be collected for drug screen at screening, weeks 4, 12, 24, 48, 72, and 96.

6.3.4 Stored sample collection

Blood samples for storage and research will be obtained at screening, total of 11 tsp, and a total of 9 tsp at weeks 4, 12, 24, 48 and 96. Samples collected will include:

- Serum storage (10 mL) SST/tiger top (2 teaspoons)
- Plasma storage (6ml) EDTA (1 teaspoon)
- DNA paxgene will be collected (8.5ml) one time at baseline (1 ½ teaspoon)
- RNA paxgene will be collected (2.5ml) (1/2 teaspoon)
- Peripheral blood mononuclear cells (30 ml) Green top/heparin (6 teaspoons)

6.3.5 Fibroscan

Patients may have assessment of liver fibrosis by transient elastography with fibroscan at screening, 24, 48 weeks, and 96 weeks.

6.3.6 HIV and HCV monitoring

HIV antibody/antigen will be checked at weeks 4, 24, 36, 48, 72, and 96 with a one month window. HCV RNA will be checked per standard of care, and subsequently at weeks 36, 48, 72, and 96 with a one month window.

6.3.7 Viral sequencing

Individuals with new seroconversion to HIV will have sample sent for viral sequencing and phylogenetic analysis. Individuals with detectable HCV RNA after completion of HCV treatment or new infection during the follow up period will have current sample, and baseline stored sample sent for viral sequencing and phylogenetic analysis. Phylogenetic analysis will enable us to demonstrate mode of transmission of new infections and resistance associated variants that may impact ART and DAA therapy in the future.

6.4 Optional Standard of Care PrEP with TDF/FTC

All eligible subjects will be offered initiation of standard of care treatment with TDF/FTC for HIV prevention from Day 0 through week 24 of HCV treatment. Patients will be seen and monitored as per standard of care. Patients who uptake PrEP will be treated for a 12 month time period, and then transitioned to a community provider. The first day of PrEP treatment will be considered day P0. See Appendix A Study Schedule.

On or after week 48, all participants enrolled in ANCHOR study will be administered a brief PrEP Retrospective questionnaire (Appendix K) to clarify why they did or did not uptake PrEP.

6.4.1 Study Labwork

Any participant who seroconverts to HIV while on PrEP treatment will have serum sample collected for sequencing and phylogenetic analysis.

6.4.2 Adherence Monitoring

On weeks P4, P12, P24, P36, and P48 participants will meet with study staff to complete counts of remaining pills, answer questions regarding PrEP treatment adherence, and provide blood samples to evaluate tenofovir levels. Tenofovir levels will be done on the first 50 participants at Month 1, Month 6 and Month 9 treatment.

6.4.3 Linkage to care

Participants will be treated for up to 12 months from the time of initiation of PrEP. As this is a chronic medication, at the end of treatment, patients interested in continuing on PrEP will be linked to care with a community provider.

Any participant who seroconverts to HIV will be immediately linked to care, in DC through the Red Carpet Entry Program, and in Baltimore through the JACQUES program.

6.5 Optional Standard of Care Opioid Substitution Therapy with Buprenorphine

All subjects who meet criteria for opioid use disorder per the DSM-V will be offered initiation of standard of care treatment with buprenorphine for treatment of opioid use disorder. Patients will be seen and monitored as per standard of care. Patients will be offered uptake from day 0 until week 24 of HCV treatment, and will be treated for a 12 month time period, and then transitioned to a community provider. The first day of buprenorphine treatment will be considered day B0. See Appendix A Study Schedule.

6.5.1 Retention Monitoring

Patients will be monitored for ongoing retention in buprenorphine program by observation of buprenorphine prescription. Documentation of buprenorphine prescription will be done at day B0 and weeks B2, B4, B8, B12, B24, B36.

6.5.2 Linkage to care

Participants will be treated for up to 12 months from the time of initiation of buprenorphine. As this is a chronic medication, at the end of treatment, patients interested in continuing on buprenorphine will be linked to care with a community provider.

6.6 Optional Geographic Momentary Assessment

All enrolled subjects in Phase 2 (participants 101-200) will be offered participation in the Geographic Momentary Assessment (GMA), an optional, exploratory outcome through a research collaboration with the National Institute of Drug Abuse (NIDA) to further explore drug use, overdose, risky behaviors, and barriers to hepatitis C treatment and PrEP.

While many patients inducted and stabilized on buprenorphine or methadone reduce or eliminate opioid use, there remains a group of individuals who continue to use opioids despite opioid agonist therapy. Additionally, there are patients in treatment who continue to use drugs other than opioids including alcohol, marijuana, stimulants among others. These individuals remain at

risk for harm including overdose, acquiring or transmitting HIV, HCV, and other diseases, and poor adherence to medical treatment.

This NIDA-developed technology, GMA, combines Ecological Momentary Assessment (EMA), the collection of real-time in the field data via smartphones, with GPS of self-reported data on craving, drug use, and stressors collected daily in real time via a cell-phone based application (APPENDIX G). Using the smartphone's GPS log, we will collect data on participants' locations throughout the day to assess how changes in environment affect mood and activities. GMA overcomes the limitations of retrospective assessments, which may not adequately measure the dynamics of craving or accurately depict the relationships between craving and use (Tiffany & Wray, 2012; Kavanagh et al., 2013; Serre et al., 2015). The GPS receiver chipsets have become ubiquitous in smartphones and, by combining GPS information with information on the strength of signals obtained from cellular data networks and wireless internet data connections (i.e., assisted GPS), smartphones can provide accurate location information more quickly than standalone GPS units and in cases where GPS signals are attenuated (e.g., indoors, in urban areas with many tall buildings) (Zandbergen, 2009; Zandbergen & Barbeau, 2011).

These assessments will be evaluated on an ongoing basis by Drs. [name] and [name] (sub-investigators on the protocol), who are nationally recognized experts in the field of GMA as it relates to substance use-disorder and drug craving. NIDA has been conducting GMA studies since 2005 and has collected data on over 850 study participants. The results of their work have been published in high-quality journals; the first paper was published in 2009 in Archives of General Psychiatry⁽³⁰⁻⁵⁷⁾. Recently NIDA used GMA to study the effects of clonidine on relapse to opioid use in patients receiving buprenorphine maintenance which was published in the American Journal of Psychiatry⁽⁴²⁾.

This exploratory outcome will parallel hepatitis C treatment and PrEP and buprenorphine/methadone treatment as indicated, without impacting the above listed research assessments or study visit schedule. Using cell phones with active data plans provided free to enrolled subjects for one year, subjects will be queried by an GMA-specific application four times per day from Day 0 – Week 24 and one-time daily from Week 25-48 to complete an assessment of drug use, craving, stress, and other social and behavioral factors as an in-depth risk assessment (see Appendix G). Subjects will have training on use of the GMA application on Day 0, and phones will be distributed. Subjects will then complete surveys on a daily basis and will return their cell phones at Week 48. These prompts will take between 5 and 8 minutes on average to complete, and will be associated with weekly remuneration if completed regularly (see section 11). Participants can briefly turn off the alerts if they are driving, showering, etc. Participants are otherwise instructed to respond, even if at work.

For participants enrolled in GMA, at their ANCHOR visits they will complete an Adherence Packet-4 at baseline. The Adherence packet-4 (APPENDIX I) consists of 4 questionnaires (total about 15 minutes) including:

1. **The Perceived Stress scale (PSS)** (Cohen et al., 1983) is a 14-item measure of self-rated stress levels and coping ability over the past month. Takes about 5 minutes (Appendix 37).

2. **HIV Knowledge Questionnaire** (Carey & Schroder, 2002). The HIV Knowledge Questionnaire is an 18-item questionnaire used to assess knowledge of HIV transmission and protective behaviors. The HIV Knowledge Questionnaire shows good internal consistencies (Cronbach's $\alpha=.75\text{-.89}$) and reliability ($r=.76\text{-.94}$). It takes about 3 minutes to complete.
3. **HIV Attitudes Scale.** The HIV Attitudes Scale is an 11-item questionnaire assessing attitudes and concerns about transmitting/contracting HIV. The questionnaire takes about 3 minutes to complete.
4. **Food, Housing, and Health Security Questionnaire (FHHSQ).** This is a condensed 8-item questionnaire including 3 questions from the **NHANES Food-Security Questionnaire** (NHANES FSQ), 4 questions from the **Housing-Security Questionnaire**, and 1 question from the **NHANES HIQ/HUQ**. It takes about 2 minutes to complete.

An Adherence Packet-2 (comprised of questionnaires 1-PSS, and 2-FHHSQ listed above) will be completed at weeks 4, 12, 24, and 48.

